12.1 Trial report

Any and all information concerning this clinical trial are to be treated as confidential. The investigator carries out the statistical analysis and draws up an integrated final report; these are then evaluated and signed by the sponsor as well as by all other responsible persons. All information contained in this report are strictly confidential.

12.2 Publications

The final results of this clinical trial shall be published in a renowned specialist journal. [name] will be lead author, PD [name] will be corresponding author. The publication or presentation of the results is to be commented and approved a priori by the investigator and the sponsor. Data protection concerning all patient data has to be safeguarded for all publications. It is not planned to publish interim or partial results. Prior to its start, the study is registered on www.clinicaltrials.gov.

13 Ethical, legal and administrative aspects

13.1 Responsibilities of sponsor and investigator

Pursuant to the AMG, the sponsor of the clinical trial assumes responsibility for launching, organising and financing the clinical trial to be conducted. In this context, sponsor and investigator ensure that the clinical trial is conducted in compliance with existing laws and regulations, pursuant to the ICH GCP guidelines (1996), the declaration of Helsinki (1996) as well as the dispositions set out in the AMG and GCP ordinance (2004). The investigator accepts the requirements of the undersigned study protocol.

Responsibilities of the investigator include amongst others:

- understanding of the properties of the trial medication described in the Investigator's Brochure or in the specialist information
- understanding and implementation of the treatment plan
- ensuring that enough time and capacities for conducting the trial are available
- correct collection and documentation of data, reporting
- supplying any and all data to the sponsor, monitor or to the respective authorities for audits and/or inspections
- ensuring that information on patients as well as all information obtained from the sponsor are treated as confidential by all persons involved in the trial.

Pursuant to the AMG, each investigator assumes responsibility for conducting the clinical trial in the trial center.

13.2 Decision of the ethics commission and notification to authorities

PD [name] (representative of the sponsor) applies to the ethics commission of the Medical University of Innsbruck and to the Austrian Federal Office for Safety on behalf of the sponsor.

13.3 Patient information and declaration of consent

Prior to the start of the trial, each patient must declare his/her consent to the investigator in writing, after first having been informed – orally and in writing – on the nature, meaning and consequences of the clinical trial in a way that is complete and understandable for him. The content of this information is documented on the declaration of consent. The patient is informed if significant new findings on the trial medication emerge during the study.

The patient's declaration of consent for the participation in the clinical trial is dated and signed by the patient as well as by the doctor. The patient receives a copy of the signed patient information/declaration of consent. The second copy is filed in the investigator site file by the doctor.

It is expressly noted that no examinations related to the study may be performed until a legally valid declaration of consent of the patient is submitted.

13.5 Data protection and obligation to secrecy

Collection, transfer, storage and analysis of personal data within this clinical trial is made pursuant to legal dispositions (Federal Data Protection Act). The prerequisite for this is the voluntary consent of the patients within the framework of the declaration of consent prior to the participation in the clinical trial. During their information on this clinical trial, the patients are informed in this regard on the following:

1. Data that is collected as part of this clinical trial is recorded on paper forms or electronic data carriers, is treated as confidential and may only be passed on, without the patients being mentioned by name (pseudonymized), to
 - the commissioner of the study in order to conduct a scientific analysis and assessment of adverse events,
 - the competent federal authority, the ethics commission of the Medical University of Innsbruck and the European Database in order to review the orderly conduction of the study as well as to evaluate study results and adverse events.
2. Insofar as it is necessary for reviewing the clinical trial, representatives of the commissioner (monitors, auditors) and/or of the competent monitoring authority who are authorized and sworn to secrecy may inspect the personal data available at the investigator. For this measure, the investigator is released from his professional obligation to secrecy.

3. The consent to the collection and processing of personal data in the framework of this clinical trial is irrevocable. A patient will be instructed that he may end his/her participation in the clinical trial at any time – without giving reasons and without facing any subsequent detriments. In case the declaration of consent is revoked, the data stored up to this point will still be used without the patient being mentioned by name, if necessary, in order to assess the effects of the medicinal product at trial and to ensure that interests of the person concerned which are worth protecting are not harmed.

14 Changes to the study protocol (amendments)

In order to ensure that broadly comparable results are obtained in all trial centers, as well as in the interest of proper data evaluation, a change to the trial conditions agreed upon and set out in this study protocol is not intended.

However, in exceptional cases changes to the trial conditions are possible. These are only made after mutual agreement has been reached between the investigator and the sponsor. Any change to the study procedure as set out in the study protocol has to be made in writing, giving the respective reasons, and has to be signed by all persons responsible for the study. The changes shall then be deemed as part of the study protocol. If necessary (e.g. when changing the medication dose and/or in case of other significant changes which indicate a direct influence on the safety of the study participants), approval of the changes to the study protocol has to be obtained from the relevant ethics commission and/or authorities as well as from the patients, and the amendment is to be submitted to the federal authority.

15 Annex

Hallux Metatarsophalangeal-Interphalangeal Scale	
Pain (40 points)	
None	40
Mild, occasional	30
Moderate, daily	20
Severe, almost always present	0
Function (45 points)	
Activity limitations	
No limitations	10
No limitation of daily activities, such as employment	7
Limited daily and recreational activities	4
Severe limitation of daily and recreational activities	0
Footwear requirements	
Fashionable, conventional shoes, no insert required	5
Comfort footwear, shoe insert	3
Modified shoes or brace	0
MTP joint motion (dorsiflexion plus plantarflexion)	
Normal or mild restriction (75° or more)	10
Moderate restriction (30°-74°)	5
Severe restriction (less than 30°)	0
IP joint motion (plantarflexion)	
No restriction	5
Severe restriction (less than 10°)	0
MTP-IP stability (all directions)	
Stable	5
Definitely unstable or able to dislocate	0
Callus related to hallux MTP-IP	
No callus or asymptomatic callus	5
Callus, symptomatic	0
Alignment (15 points)	
Good, hallux well aligned	15
Fair, some degree of hallux malalignment observed, no symptoms	8
Poor, obvious symptomatic malalignment	0
Total=	100
American Orthopaedic Foot and Ankle Society	
From: http://www.aofas.org/i4a/pages/index.cfm?pageid=3494	

VRS for Pain

no pain 0 1 2 3 4 5 6 7 8 9 10 worst possible pain

VRS for overall satisfaction with operation / pain management

not satisfied 0 1 2 3 4 5 6 7 8 9 10 very satisfied

16 Literature

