3.3 Secondary endpoint of the study

The need for rescue pain medication, the patients' satisfaction with surgery and pain therapy (collected by means of VRS) and the clinical outcome (collected by means of AOFAS forefoot score) were defined as parameters of secondary objective. Furthermore, the occurrence of UAEs and AEs as well as the need for rescue pain medication is collected.

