6.1 Visit 1 (baseline, day 0)

Prior to admission to the clinical trial, every patient must be informed in detail on the study. Information takes place in person by the treating doctor and in writing by means of the patient information. Only after all questions of the patient have been answered, he/she will be asked to sign two copies of the declaration of consent and to personally date it. Following this, the patient receives a copy of the patient information/declaration of consent; the second copy is kept in the investigator site file.

Upon visit 1, demographic data (age, sex, weight, size, BMI, side) is recorded. Furthermore, physical examination is carried out, including examination of the range of motion (ROM) of the hallux metatarsophalangeal joint (GZGG) as well as assessment of AOFAS forefoot score by means of the "AOFAS Hallux Metatarsophalangeal-Interphalangeal Scale" questionnaire and the average and maximum VPRS. Women of childbearing age undergo laboratory testing to exclude pregnancy. After final examination of the inclusion and exclusion criteria, the patient is admitted to the study, including his admission to one of the two treatment groups according to randomization as explained above.

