6.6.1 Assessment of effectiveness

Effectiveness is assessed by the care-taking nursing staff – which is blinded as regards the therapy group – collecting data concerning the VPRS for pain during the patient's stay in hospital which is repeated every 4 hours. For this, the patient indicates the current pain level on a scale ranging from 0 - 10 (0 meaning no pain, 10 meaning the maximum pain imaginable).

Before surgery and in the course of the postsurgical outpatient follow-ups, the respective care-taking doctor assesses not only the pain level by means of VPRS for pain but also the ROM of the hallux metatarsophalangeal joint. Furthermore, upon visit 1 and 5, AOFAS forefoot score is assessed by means of the „AOFAS Hallux Metatarsophalangeal-Interphalangeal Scale“ question-

naire (see annex) and patient satisfaction is assessed by means of VRS.

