8.1 Case report form (CRF)

Any and all patient data and examination results shall be entered into the CRFs (Case Report Forms) specifically created for this study.

The case report forms may only be completed with a **black ballpoint pen**. Corrections are to be made in such a way that old entries remain legible (it is not allowed to use correction products). Corrections are to be signed and dated by the authorized person who makes the corrections. Data which is not available or which has not been collected, has to be clearly marked as such (NA or ND). The reasons to do so should be documented, if necessary.

The investigator ensures that any and all patients' data is entered into the CRFs immediately, legibly, completely, correctly and in accordance with the patients' files.

The monitor serves the completed original pages after they have been checked for plausibility and completeness on the sponsor; a copy remains with the investigator and is stored for 15 years.

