9.2 Audit

In order to guarantee that the trial is conducted pursuant to GCP guidelines, internal (e.g. by the sponsor) and external (e.g. by the authorities) audits may be conducted. The auditor is independent vis-à-vis the employees who are involved in the trial.

During the audit, the following points are checked, amongst others:

- conduction of the trial according to the study protocol
- validity of data
- quality of trial pursuant to GCP guidelines.

Following every external audit, the investigator receives an audit confirmation by the auditor. This confirmation must be kept in the investigator site file in order to have it at disposal in case of an inspection by the authorities. The audit report is transmitted to the study sponsor. At the end of the trial, an audit certificate is enclosed to the final report. In addition, authorities may conduct audits and inspections pursuant to the Austrian Medicinal Product Act.

10 Data entry and data management

Study with paper-based documentation

Data is managed and processed by the data manager by means of the software SPSS Statistics (company IBM, Armonk, New York, USA) and Excel (company Microsoft, Redmond, WA, USA).

Data is validated by the programmed range, validity and consistency checks. Additionally, there is a manual/visual check for medical plausibility pursuant to the requirements of GCP. If necessary, queries may occur which are to be transmitted to the respective trial center on special forms. On the basis of the forms, the investigator has to review and answer those discrepancies. These forms are then returned to data management where those discrepancies are corrected in the database accordingly. The forms are stored together with the case report form at the trial center and by data management.

Upon study completion, the database is closed after all entries have been entered and all queries have been resolved. This process is documented.

11 Statistics

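### As printed in the annex, the AOFAS function items reach at most 40 points against a stated 45, so the form reaches at most 95 against a stated 100

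*Combined protocol and SAP*

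**What the plan says.** Section 15 (Annex) prints the AOFAS Hallux Metatarsophalangeal-Interphalangeal Scale in three blocks, headed "Pain (40 points", "Function (45 points" and "Alignment (15 points" (each heading closes its bracket in the annex). It states a total of 100 and credits a web page of the society that issued the scale.

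The form is not background material. Section 6.6.1 states that "upon visit 1 and 5, AOFAS forefoot score is assessed by means of the" questionnaire of that name, and points to the annex. Sections 6.1 and 6.5 name the same questionnaire for the baseline and final visits; 6.1 lists the physical examination "as well as assessment of AOFAS forefoot score by means of the" scale.

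Section 3.3 makes the result a secondary endpoint: "the clinical outcome (collected by means of AOFAS forefoot score) were defined as parameters of secondary objective". Section 11.3.1 lists it again among the secondary effectiveness variables, and section 11.3.3 limits the secondary variables to description.

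**The concern.** A summed score has meaning only against its range. If the items under a heading cannot produce the points the heading promises, then a patient with the best possible answer to every item still falls short of the stated maximum. A reported mean would be read as points out of 100 although the form that produced it stops lower.

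At stake is the interpretation of absolute AOFAS values, and any comparison with values from a form that does run to 100. The same form serves both arms and both visits, so the gap does not in itself favour either arm.

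**Working it through.** **Inputs.** All come from the form in section 15 (Annex).

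| Block | Item | Points printed | Best answer |
|---|---|---|---|
| Pain | single item | 40 / 30 / 20 / 0 | 40 |
| Function | activity | 10 / 7 / 4 / 0 | 10 |
| Function | footwear | 5 / 3 / 0 | 5 |
| Function | MTP motion | 10 / 5 / 0 | 10 |
| Function | IP motion | 5 / 0 | 5 |
| Function | stability | 5 / 0 | 5 |
| Function | callus | 5 / 0 | 5 |
| Alignment | single item | 15 / 8 / 0 | 15 |

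**Step 1: reproduce the stated total.** Sum of the three headings: 40 + 45 + 15 = 100. The stated total follows from the headings.

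**Step 2: compare each block with its heading.** Block maximum = sum of the best answers in the block.
- Pain: 40, heading 40. Agrees.
- Alignment: 15, heading 15. Agrees.
- Function: 10 + 5 + 10 + 5 + 5 + 5 = 40, heading 45. Short by 45 − 40 = 5.

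**Step 3: attainable total.** 40 + 40 + 15 = 95, against 100. The shortfall of 5 is the function shortfall and nothing else. It is 5/45 = 11.1% of the stated function points and 5/100 = 5% of the stated total.

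**Step 4: what each possible cause would mean for a score.** The documents do not decide between these.
- *One 5-point item is missing.* Restoring it gives 40 + 5 = 45 and 95 + 5 = 100, so heading and total both hold. Each patient loses whatever that item would have scored, so totals are 0 to 5 points too low.
- *One item carries too few points.* Its top answer scores 5 too low, and heading and total again hold. The effect on intermediate answers cannot be determined. Purely as an illustration, suppose the footwear item's top answer were meant to be 10. Its printed middle answer of 3 could then belong anywhere from 0 to 10, which puts a patient giving that answer between 10 − 3 = 7 points too low and 3 − 0 = 3 points too high.
- *The function heading is wrong and should read 40.* The headings then sum to 40 + 40 + 15 = 95, so the stated total must change too. Scores are unaffected and only the stated maximum is wrong.

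**The case against.** The strongest reply accepts the sums and disputes their reach. The text was read from PDF by a program and tables may be broken. Each function item does run down to 0 with no stray label or number, but this is weak reassurance: a misread top value would still run down to 0, and a whole item lost would leave the others intact. Because the headings and the total agree with each other, a fault in a single row is at least as plausible as an error in the plan.

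Nor do the documents show the form on which data were captured. Section 8.1 says "Any and all patient data and examination results shall be entered into the CRFs", which were made for this trial and are not included. The CRF version may be correct. Finally, the endpoint is descriptive and no test or threshold uses the total.

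All of this stands, and it limits the point to the form as printed. It does not remove the mismatch: nothing elsewhere in the documents reconciles 40 with 45 or 95 with 100, and section 6.6.1 sends the assessor to this form.

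Two stronger readings are tempting and are not supported:
- A reader might infer that the planned data checks would let the fault through, since section 10 says "Data is validated by the programmed range, validity and consistency checks" and every total from 0 to 95 lies inside 0 to 100. Section 10 gives no limits, so no defect in those checks can be shown.
- A reader might infer that every AOFAS score is 0 to 5 points too low. That range holds only for a missing 5-point item. It is not established for a mis-weighted item, and it is wrong if the heading and total are at fault.

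**Conclusion.** The point holds as a minor inconsistency. Confidence is high for the arithmetic on the form as printed. It is not high for the proposition that the trial's working form had the fault, because that depends on a CRF not seen and on the table having been read correctly from the PDF.

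The size is 5 points in the function block and in the total; what that does to an individual score depends on the cause. The statements by cause in the working assume a single fault, in one item or in the heading with its total. The primary pain endpoint, its t-test and the sample size do not use this score.

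The visit plan's date for the final visit (day 24 ± 7, against day 42 ± 7 in the synopsis and section 6.5) is a separate discrepancy, to be reconciled as its own point. It adds no weight here.

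**What to change.** Before any AOFAS scoring, compare three things: the annex form on the PDF page, the CRF version, and the source the annex cites. Then act on the cause found:

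- If an item's points are wrong, correct them in the annex and, where affected, in the CRF. Re-score completed forms if item-level answers were kept.
- If an item is missing, add it. Forms completed without it have no answer to re-score, so report those scores with the true maximum of the version used (95 for the form as printed).
- If the heading is wrong, correct both the heading and the total.
- If item-level answers were not kept and re-scoring is impossible, report the scores with the true maximum of the version used.
- If only the machine-read text is at fault, no change is needed.

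The cost is one check against the cited source and one corrected form. Re-scoring adds some work, and whether it is possible cannot be judged without the CRF. The analysis plan needs no change beyond stating the score's maximum when it is reported.
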